psychiatry, psychology, or behavioral modification. Information on PHQ-9 scores, referrals, patient's uptake (or decline) of prescribed treatments are also captured by our EMRs. Any clinical diagnosis and treatment of depression for those not captured by the screening will also be identified through EMRs. During the glucola visit (22-24 weeks of gestation), all women will be screened for depression a second time using the same screening process as the first prenatal visit.

Women being treated for depression before the screening will be identified (<2%) and analyzed as a separate group.

Depression severity will also be used for stratification (to control for confounding by indication) when conducting head-to-head comparison of treatment effect among various treatment options.

Depression type (with or without other psychiatric comorbidity) will be determined by identifying concurrent psychiatric disorders from KPNC EMRs including organic psychotic conditions, other psychoses, neurotic and personality disorder and other mental disorders. The expected number of women who have depression only and depression with comorbidity during the study period is listed in Figure 2.

Antidepressant use during pregnancy. Antidepressant use, including types, timing, and duration of use, will be ascertained both through the depression screening and EMR (i.e., pharmacy database). The KPNC pharmacy database captures all inpatient and outpatient prescriptions and dispensations. Because of a large financial incentive to obtain medications at KPNC (in most cases, medications are covered with minimal co-payments), the KPNC pharmacy database has been shown to capture 93-98% of prescription medications of varying types. Compliance of taking antidepressants will also be ascertained during interview.

Psychotherapy. KPNC EMR records any psychotherapy patients receive for depression. The information includes the type of therapies (individual or group), sources of the treatment (psychologist, behavioral modification specialist, or psychologist/social worker) and number of sessions attended.

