5 COMPARATORS

Comparators will vary depending on the research questions to be examined in analyses. The overall objective is to use appropriate comparators so that correct results of comparative effectiveness can be obtained after disentangling treatment effect from the effect of underlying depression (confounding by indication), and treatment benefits after balancing treatment benefit against the simultaneous risk of side effect (e.g., use of antidepressants). The following four cohorts (A-D) will be established within each depression type (depression only or depression with comorbidity) and various comparators will be used to answer the research questions in the Specific

Aims. We will also establish a control cohort (E) of women without depression for comparison of baseline risk.

Cohort A: women who screened positive and used antidepressants only. All women who screened positive for depression and were subsequently prescribed antidepressants during pregnancy will form Cohort A. Comparison of this cohort to Cohort D, a comparator for Specific Aim 1, will demonstrate the treatment effect of antidepressant use in reducing the fetal risk after controlling for severity of depressive symptoms and other confounders. Comparisons to Cohort B or C, comparators for Specific Aim 2, will determine which treatment option (antidepressant use, psychotherapy or combination therapy) is more effective in reducing fetal risk or has a better risk-benefit profile (pair-wise comparisons). Results from such comparisons will provide valuable information for clinicians as well as pregnant women to make an informed decision on the treatment options for depression during pregnancy based on research evidence.

Cohort B: women who screened positive and received psychotherapy only. This cohort consists of women who screened positive and subsequently received psychotherapy during pregnancy, but did not take any antidepressants. Comparison to Cohort D will determine if mitigation of depression by psychotherapy reduces fetal risk, after controlling for depression severity. Comparisons of this cohort to antidepressant use (Cohort A) or combination therapy (Cohort C), two separate comparators for Specific Aim 2, will provide head-to-head assessment of comparative effectiveness of treatment regimens.

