Cohort C: women who screened positive and used both antidepressants and psychotherapy. This will be a cohort similar to Cohort A and B except that women in this cohort received combination therapies after screening positive. We classify them in a separate cohort to make Cohorts A and B encompass more clearly defined exposures of antidepressants and psychotherapy (pure exposure groups). In addition, this cohort may allow us to examine the potential benefit of combination therapy. Like Cohorts A and B described above, they will be compared to untreated comparator (Cohort D) for Specific Aim 1 and other treatment comparators (Cohort A and B) for Specific Aim 2.

Cohort D: women who screened positive for depression, and did not obtain treatment. Pregnant women whose PHQ-9 score is ≥ 10 at either of two screening visits (the first prenatal visit and glucola visit) or who were diagnosed as having depression by their medical providers, but did not receive any treatment for depression during pregnancy, will be classified into this cohort. Comparison of this cohort to Cohort E (control cohort), a comparator for Specific Aim 3, will allow us to assess whether untreated depression during pregnancy increases fetal risk (i.e., PTD or LBW) without the interference of treatment effect. We can also examine potential dose-response relationships based on the severity of depression (PHQ-9 scores) and duration of depression (persistence of the symptoms in both screening visits vs. at only one of the visits). Importantly, this cohort can be used as a comparator for Cohorts A, B, and C to examine the effect of depression treatment after controlling for underlying depression and severity (untreated comparators).

Cohort E (controls): women who screened negative for depression in both visits and did not receive treatments for depression. This cohort consists of the largest number of pregnant women, those who have neither depression and concurrent psychiatric comorbidity, nor treatment during pregnancy. This cohort will serve as the comparator for determining the effect of untreated depression on fetal risk (i.e., PTD, LBW). It will also serve as a reference check for other

comparisons. For example, does the benefit of a treatment totally eliminate the risk of PTD associated with depression during pregnancy?

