The categorization into each cohort will be finalized at the end of pregnancy based on whether a woman met the criteria throughout the pregnancy. Comparisons of Cohort A, B, C, vs. D respectively, will answer the question of whether treating depression during pregnancy improves fetal outcomes, reducing PTD or LBW associated with untreated depression after controlling for underlying depression severity. Pairwise comparisons among Cohort A, B and C will answer the question of which treatment is most effective in improving fetal outcomes and has the best risk-benefit profile.

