6 ANALYTIC METHODS

6.1 General Approach to Analyses

While all eligible pregnant women will be included in the registry after their pregnancies are identified, the follow-up time for all pregnancy outcomes of interest will start at 20 weeks of gestation because, by definition, PTD and LBW among live births occur after 20 weeks of gestation. All pregnancies ending before 37 completed weeks (259 days) will be considered as failure (PTD). As in our previous studies, we will use the Cox proportional hazards regression model, accommodating delayed entry into the cohort^{76,77}. Birthweight for all newborns will be obtained from EMR and analyses for LBW will utilize logistic regression.

The study design can be characterized as two-stage. Unlike typical applications of two-stage sampling in epidemiologic studies, where the stage-two sample is selected on the basis of both exposure (or exposure surrogate) and outcome (e.g. two-stage case-control sampling), only exposure status will be known at the time of stage-two sampling to keep the nature of a cohort study design. However, study outcomes of interest will eventually be measured on all 88,000 stage-one units, and there is much to be gained by utilizing all available information in estimation of associations of interest (see Sample Size and Statistical Power section).

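### The main treatment contrasts use cohort labels fixed at delivery while follow-up starts at week 20, so late treatment starts can look protective; entry and time-dependent coding need defining for these contrasts

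*Combined protocol and SAP*

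**What the plan says.** All references are to the combined protocol and SAP.

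- **Labels.** Section 5 (Comparators): "The categorization into each cohort will be finalized at the end of pregnancy based on whether a woman met the criteria throughout the pregnancy". Section 4.1.3 (Stage II samples) adds that changes after the initial assignment are settled at analysis.
- **Treated cohorts.** Section 5: "All women who screened positive for depression and were subsequently prescribed antidepressants during pregnancy will form Cohort A". No latest start week is given for A, B or C.
- **Untreated cohort.** Section 5 places in D women with a positive screen, "or who were diagnosed as having depression by their medical providers", provided that they "did not receive any treatment for depression during pregnancy, will be classified into this cohort".
- **Time zero.** Section 6.1: "the follow-up time for all pregnancy outcomes of interest will start at 20 weeks of gestation". The same paragraph says "we will use the Cox proportional hazards regression model, accommodating delayed entry into the cohort", without saying which date is the entry date.
- **Screens.** Section 3.1.3: "During the glucola visit (22-24 weeks of gestation), all women will be screened for depression a second time". On prior treatment: "Women being treated for depression before the screening will be identified"; these women form a separate analysis group.
- **Models.** Section 6.1, Aim 1, estimates hazard ratios for A, B and C against D. Aim 2 takes its pairwise contrasts from that model. Time-dependent covariates appear under Aim 1 only for dose, duration, number of sessions and timing. Low birthweight (LBW) uses logistic regression.

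**The concern.** A woman first positive at the second screen and not already treated can start treatment only after follow-up has begun. To be labelled A, B or C she must stay pregnant long enough to start. If she delivers preterm first, her event goes to D. If she starts later, her time from week 20 counts as treated although no event was possible in it under that label. Cohort C needs two starts, so it gains most, and a woman who delivers before her second treatment stays in A or B.

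This is immortal-time bias. It favours treatment over no treatment and combination over single therapy, which are the questions of Aims 1 and 2. Adjustment for baseline PHQ-9 and propensity scores deals with who is treated, not when. The LBW logistic model shares the problem and has no time axis on which to correct it.

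**Working it through.** **1. The plan's own scale.** Section 6.2.2 gives detectable hazard ratios for preterm delivery (PTD) of 1.69-1.83 (400 per cohort) and 1.32-1.38 (effective 1,600 per cohort), for PTD rates of 8-11%, two-sided alpha 0.05 and power 80%. I used HR = exp[(1.960 + 0.842)/√(0.25 × events)], with events = n[r + 1 − (1 − r)^HR].

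- n = 1,600, r = 8%: 302 events, HR 1.38. r = 11%: 404 events, HR 1.32.
- n = 400: 1.82 and 1.69.

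The figures reproduce to within 0.01. On the protective side, 1/1.32 = 0.76 and 1/1.38 = 0.72.

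**2. Assumptions for the bias.** The documents give no start weeks, so all of these are assumed:

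- no treatment effect, PTD 10% in every group, all women identified before week 20;
- preterm gestational age = 20 + 17 × Beta(5,1) or 20 + 17 × Beta(10,1), which puts (14/17)^5 = 38% or (14/17)^10 = 14% of PTD before week 34;
- 30-50% of women intended for treatment, and 20-40% of those for both treatments;
- 25-50% of starts late, uniform from week 22 to week E (28, 32 or 36); other starts by week 20; the two starts independent.

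**3. One case by hand.** Take 1,000 depressed women: 500 never treated, 400 intended for one treatment, 100 for both; half of starts late; Beta(5,1). Let u be the share of the late-start window still to come at delivery. Then

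- m1 = E[u] = [(E−20)^6 − 2^6] / [6 × 17^5 × (E−22)]
- m2 = E[u²] = 2/(E−22)² × [(E−20)^7/42 − 64(E−20)/6 + 128/7] / 17^5

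Each planned start has happened by delivery with probability 1 − 0.5u. The preterm births by final label are

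- C: 10(1 − m1 + 0.25 m2)
- A or B: 40(1 − 0.5 m1) + 10(m1 − 0.5 m2)
- D: 50 + 40 × 0.5 m1 + 10 × 0.25 m2

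The term births are 90, 360 and 450.

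| E | m1 | m2 | C | A/B | D | Risk C | Risk A/B | Risk D | C/D | C/(A/B) |
|---|---|---|---|---|---|---|---|---|---|---|
| 28 | 0.0051 | 0.0020 | 9.95 | 39.94 | 50.11 | 9.96% | 9.99% | 10.02% | 0.99 | 1.00 |
| 32 | 0.0351 | 0.0120 | 9.68 | 39.59 | 50.73 | 9.71% | 9.91% | 10.13% | 0.96 | 0.98 |
| 36 | 0.1407 | 0.0459 | 8.71 | 38.36 | 52.93 | 8.82% | 9.63% | 10.52% | 0.84 | 0.92 |

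The true ratio is 1 throughout. The week-36 row, solved as a Cox model, gives C vs D 0.826.

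**4. All 48 combinations.** Cox hazard ratios from expected daily risk sets, weeks 20-37, labels fixed at delivery:

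| Late starts end by | C vs D | A/B vs D | C vs A/B |
|---|---|---|---|
| Week 28 | 0.993-1.000 | 0.996-1.000 | 0.995-1.000 |
| Week 32 | 0.954-0.998 | 0.976-1.000 | 0.966-0.999 |
| Week 36 | 0.826-0.969 | 0.908-1.000 | 0.866-0.980 |

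With treatment coded as time-dependent, C vs D is 1.00 in every cell.

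**5. Against the detectable effect (log scale).** A spurious 0.95 is ln 0.95/ln(1/1.38) = 16% to ln 0.95/ln(1/1.32) = 18% of it. A spurious 0.83 is 58% to 67%.

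**6. Sensitivity to PTD timing.** A second calculation (PTD 9.5%, any treatment vs D, 20-50% intended, half of starts by week 20 and half over weeks 24-36) gives 0.90-0.93 when 23% of PTD falls before week 34, and 0.78-0.85 when 48% does. The ranges in step 4 are therefore not bounds.

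**7. LBW.** For the week-36 row, assume LBW in 50% of preterm and 2.5% of term births. C: 8.71 × 0.5 + 90 × 0.025 = 6.61 of 98.71. D: 52.93 × 0.5 + 450 × 0.025 = 37.72 of 502.93. Odds ratio = (6.61/92.10)/(37.72/465.21) = 0.88, with no true effect.

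**The case against.** - **The plan already has the tools.** A reader might infer that it has no entry or time-dependent rule at all. That is not so: section 6.1 names both. What is missing is the entry date and the use of time-dependent treatment in the main contrasts. Delayed entry alone would not be enough. In the second calculation, entering treated women at treatment start while D stays labelled at delivery still gave 0.89-1.00 with PTD concentrated near term.
- **Most treatment may start early.** Section 4.1.3 expects stage-two women to be selected, with treatment status known, mostly before the third trimester (taken here as about week 28). If so, and if identification is early, the bias is close to nil. This stands as a reason not to assume a large effect. It gives no start weeks, however, and the same section allows later changes of status. The week-36 figures have no support in the documents beyond the absence of a start limit.
- **A planned check might show it.** Aim 1 tests the interaction of exposure with gestational age, in the stage-two sample. That could flag the pattern but does not correct it. The instrumental variable analysis is a sensitivity analysis for unmeasured confounding.
- **Direction.** Section 5 describes A-C as screen-positive but lets provider-diagnosed women into D. A reader might infer that late-diagnosed women enter only D, which could offset or reverse the bias. The documents lean the other way: section 3.1.3 captures diagnosis and treatment outside the screens, section 4.1.1 defines A-D by being depressed, and section 7.1.1 classifies by diagnosis and treatment. The wording needs reconciling, but a reversal is not supported.

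**Conclusion.** The concern holds and should be fixed; confidence is medium. Following the plan as written builds immortal time into the A, B and C vs D contrasts and the C vs A or B contrasts, in favour of treatment and of combination therapy. Whether this matters in practice turns on when treatment starts: negligible if late starts end by about week 28, a few percent by week 32, and up to 17% on the hazard ratio for C vs D in the most extreme week-36 cell. These sizes rest on the assumed start windows, shares treated, PTD timing and early identification.

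The documents do not support saying that the results will be biased by any particular amount. They support saying that a modest treatment effect could not be told apart from this artefact in the main result unless start dates are used.

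**What to change.** 1. In the primary Aim 1 and Aim 2 Cox models, define entry as the later of week 20 and the date depression was first identified.
2. Code treatment (none, antidepressant, psychotherapy, both) as time-dependent from its recorded start, moving a woman from A or B to C when the second treatment starts. This extends what Aim 1 already plans for dose and timing.
3. For LBW, classify treatment at one prespecified gestational landmark after the second screen, among women identified and still pregnant then.
4. Reconcile the screen-positive wording in section 5 with sections 3.1.3, 4.1.1 and 7.1.1, so that one identification rule applies to A-D.
5. Report the gestational week of identification and of first and second treatment start, by cohort.

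**Cost.** No new data: screening results, diagnoses and treatment timing are already to be collected. No PTD event in A-D is lost, because identification precedes delivery. Programming is real work, since section 6.1 leaves the Cox model to be implemented by the user in the two-stage software.

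The landmark excludes some women and dilutes the LBW contrast. As an example, take a week-26 landmark with 50% intended for one treatment and half of starts uniform over weeks 22-36. Women who start later are 0.5 × 0.5 × 10/14 = 0.179 of the total, out of 0.5 + 0.179 = 0.679 classed untreated, or 26%. If later treatment had its full effect, a true odds ratio of 0.75 would show as about 0.75/(1 − 0.26 × 0.25) = 0.80.

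Confounding from worsening after baseline remains, because severity is adjusted as measured before treatment.

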6 ANALYTIC METHODS

6.1 General Approach to Analyses

While all eligible pregnant women will be included in the registry after their pregnancies are identified, the follow-up time for all pregnancy outcomes of interest will start at 20 weeks of gestation because, by definition, PTD and LBW among live births occur after 20 weeks of gestation. All pregnancies ending before 37 completed weeks (259 days) will be considered as failure (PTD). As in our previous studies, we will use the Cox proportional hazards regression model, accommodating delayed entry into the cohort^{76,77}. Birthweight for all newborns will be obtained from EMR and analyses for LBW will utilize logistic regression.

The study design can be characterized as two-stage. Unlike typical applications of two-stage sampling in epidemiologic studies, where the stage-two sample is selected on the basis of both exposure (or exposure surrogate) and outcome (e.g. two-stage case-control sampling), only exposure status will be known at the time of stage-two sampling to keep the nature of a cohort study design. However, study outcomes of interest will eventually be measured on all 88,000 stage-one units, and there is much to be gained by utilizing all available information in estimation of associations of interest (see Sample Size and Statistical Power section).

Regression parameter estimates and associated standard errors will be obtained via semiparametric maximum likelihood⁷⁸, utilizing exposure and outcome measurements on all 88,000 stage-one units in addition to confounder/effect modifier measurements on the subset sample at stage-two (N=3,600). Scott and Wild presented a unified method for fitting arbitrary regression models to a large class of missing data and/or response selective sampling problems. These applications are generally characterized as: 1) a set of easily-obtainable variables is measured on a sample of N individuals; one or more of these variables are to be used as explanatory in the regression model (e.g. depression and treatment status), or are informative surrogates for “expensive” variables to be measured on a subsample; 2) the response variable is obtained for all N individuals (e.g. PTD, LBW); and, 3) a set of “expensive” explanatory variables (e.g. potential confounders/effect modifiers) are measured on a subsample. Software (R language) has been developed and available from the authors, with functions for various regression models including binary regression, linear regression for continuous response, and clustered binary data. The associated software documentation provides details on key parts of the system enabling users to implement new regression models (e.g. Cox). We will utilize logistic and Cox regression to address the study aims, as described below.

Each set of analyses addressing Aims 1, 2 and 3, outlined below, will be conducted in samples of women with and without other psychiatric comorbidities (Aim 4).

Aim 1. Treatment effect compared to untreated depression (Cohort A, B & C vs. Cohort D)

Point and interval estimates of the relative hazard of PTD associated with each treatment modality (A, B, C), relative to no treatment (D) will be calculated via semiparametric maximum likelihood estimates of Cox proportional hazards regression parameters, with adjustment for potential confounders, as described above. In determining potential confounders in our regression models, we will first examine risk factors that may be plausibly linked to depression and PTD. Inclusion of potential confounding factors in our final regression models will be evaluated based on comparison of adjusted and unadjusted relative hazard ratios⁷⁹. Departures from model assumptions will be assessed via diagnostic plots of weighted residuals and tests for interaction between exposure and time (gestational age). The assessment of confounding variables for inclusion in regression models and testing of model assumptions will be performed in the stage-two sample using standard software for fitting Cox regression models. After determining the appropriate set of confounders and that there are no departures from model assumptions, the stage-one information on primary exposure and outcome will be incorporated using the semiparametric maximum likelihood estimator. This process applies to analyses of the remaining aims.

These comparisons will allow us to assess possible treatment effects on reducing PTD through both pharmacotherapy and psychotherapy. When compared to untreated (Cohort D), the comparison will be made after controlling for underlying severity of depression as measured by PHQ-9 scores or clinical diagnosis of severity before treatment. Table 2 shows that depression severity is relatively comparable among comparison groups, allowing control for confounding by indication (underlying depression severity, a unique strength of the proposed study due to the availability of PHQ-9 scores through the universal depression screening).

We will also examine the possible dose-response in the association between antidepressant use and PTD by examining dosage of use, duration of the use, and timing of effect (single vs. multiple trimesters), in the context of time-dependent covariates. Similarly, we will also assess any dose-response relationship in the association between psychotherapy and PTD (the number of sessions received) and the effect of timing of treatment, also both as time-dependent covariates. If sample sizes allow, we will also examine the effect of combination of dose and timing (e.g., dose-response during early and late pregnancy). In addition, we will examine difference in the type of antidepressants (SSRI vs. non-SSRI).

Analyses of LBW as the outcome will parallel those described above for PTD, but logistic regression techniques will be used rather than Cox regression.

Aim 2. Head-to-head comparison of treatment regimens among Cohorts A, B & C, respectively

We will obtain point and interval estimates of relative hazards of PTD associated with the three pairwise contrasts among the three treatment groups. These estimates, and associated tests of significance, will be obtained using the Cox proportional hazards regression model developed in addressing Aim 1, fully adjusted for potential confounders including depression severity, as described above, via transformed linear contrasts of treatment group associated regression parameters. Based on the results of Aim 1 analyses of dose-response, we will obtain confounder adjusted relative hazards associated with PTD with levels of dose of a given treatment modality

(e.g. antidepressants, <30 days, 30-120 days, > 120 days duration during pregnancy), vs. particular levels of dose of another treatment (e.g. psychotherapy, ≥ 4 visits that has shown to be effective). We would categorize the comparator treatment (e.g., psychotherapy), based on the Aim 1 findings that the effectiveness of the comparator treatment in reducing risk of PTD varied by dose (e.g. no effect for < 4 visits).

As a secondary (exploratory) analysis, we will evaluate the treatment effectiveness separately for those with more severe underlying depression before treatment vs. those with more mild depression. Treating depression may be more beneficial for those with severe depression.

Analyses of LBW as the outcome will parallel those described above for PTD, but logistic regression techniques will be used rather than Cox regression.

Aim 3. Risk of PTD & LBW for untreated depression (Cohort D vs. E)

Cox proportional hazards regression will be used to obtain point and interval estimates of the hazard ratio for PTD associated with untreated depression, vs. no depression, with adjustment for potential confounders, as described above. Parameter estimation, the approach to inclusion of potential confounders and model diagnostics are as described above for Aim 1 analyses.

To evaluate potential dose-response relationships, we will examine the strength of the association between PTD and severity of depressive symptoms. Severity will be based on results of the KPNC universal screening and clinical diagnosis of depression from the KPNC EMR. Those with a clinical diagnosis of depression will be considered to be the most severe cases followed by those who screened positive with PHQ-9 higher scores (e.g., > 20). Those who screened positive, but with lower PHQ-9 scores (10-19) will be considered to have moderate depression. The effect of severity will also be examined in terms of duration.

Analyses of LBW as the outcome will parallel those described above for PTD, but logistic regression techniques will be used rather than the Cox model.

Aim 4. Difference in treatment effectiveness by depression type (with and without comorbidity)

Analyses of Aims 1, 2 and 3, will be initially stratified by depression type, with or without other psychiatric comorbidity (yes/no). Heterogeneity in treatment effectiveness by depression type will be assessed by inclusion of appropriate cross-product (interaction) terms in regression models outlined above, using a likelihood ratio test. If there is evidence of heterogeneity, point and interval estimates of relative hazards/odds ratios of interest by comorbidity status (yes/no), adjusted for confounders, will be obtained via linear combination of regression parameter estimates (main effect and interaction terms, as appropriate).

